## **COLLECTION OF PREGNANCY INFORMATION:**

### **Male participants with partners who become pregnant**

- The Investigator will attempt to collect pregnancy information on any male participant's female partner who becomes pregnant while the male participant is in this study. This applies only to male participants who receive study intervention.
- After obtaining the necessary signed informed consent from the pregnant female partner directly, the Investigator will record pregnancy information on the appropriate form and submit it to the Sponsor within 24 hours of learning of the partner's pregnancy. The female partner will also be followed to determine the outcome of the pregnancy. Information on the status of the mother and child will be forwarded to the Sponsor. Generally, the follow-up will be no longer than 6 to 8 weeks following the estimated delivery date, but may last longer according to local regulations. Any termination of the pregnancy will be reported regardless of fetal status (presence or absence of anomalies) or indication for the procedure.

### **Female participants who become pregnant**

- The Investigator will collect pregnancy information on any female participant who becomes pregnant while participating in this study. The initial information will be recorded on the appropriate form and submitted to the Sponsor within 24 hours of learning of a participant's pregnancy.
- The participant will be followed to determine the outcome of the pregnancy. The Investigator will collect follow-up information on the participant and the neonate, and the information will be forwarded to the Sponsor. Generally, follow-up will not be required for longer than 6 to 8 weeks beyond the estimated delivery date but may last longer according to local regulations. Any termination of pregnancy will be reported, regardless of fetal status (presence or absence of anomalies) or indication for the procedure.

- Any pregnancy complication or elective termination of a pregnancy for medical reasons will be reported as an AE or SAE.
- A spontaneous abortion (occurring at <22 weeks gestational age) or still birth (occurring at >22 weeks gestational age) is always considered to be an SAE and will be reported as such.
- Any post-study pregnancy related SAE considered reasonably related to the study intervention by the Investigator will be reported to the Sponsor as described in [Section 8.3.4](#). While the Investigator is not obligated to actively seek this information in former study participants, he or she may learn of an SAE through spontaneous reporting.

Any female participant who becomes pregnant while participating in the study will discontinue study intervention.

## 10.5 APPENDIX 5: GENETICS

- A genetic variation may impact a participant's response to study intervention, susceptibility to, and severity and progression of disease. Variable response to study intervention may be due to genetic determinants that impact drug absorption, distribution, metabolism, and excretion; mechanism of action of the drug; disease etiology; and/or molecular subtype of the disease being treated. Therefore, where local regulations and IRB/IEC allow, a blood sample will be collected for DNA analysis from consenting participants.
- DNA samples will be used for research related to germline mutations linked to the treatment outcome. The genetic research will consist on the analysis of the entire exome of the patient's genome.
- DNA samples will be analyzed for the germline mutations study by whole exome sequencing.
- The samples will be analyzed to study the genetic factors involved in the response to the study intervention to understand the related conditions to the patient's outcome.
- The results of genetic analyses may be reported in the clinical study report (CSR) or in a separate study summary.
- The Sponsor will store the DNA samples in a secure storage space with adequate measures to protect confidentiality.
- The samples will be retained but no longer than 15 years after the end of the study or other period as per local requirements.

## 10.6 APPENDIX 6: LIVER AND OTHER SAFETY: SUGGESTED ACTIONS AND FOLLOW-UP ASSESSMENTS

Not Applicable for this study.

## **10.7 APPENDIX 7: AES, ADES, SAES, SADES, USADES AND DEVICE DEFICIENCIES: DEFINITIONS AND PROCEDURES FOR RECORDING, EVALUATING, FOLLOW-UP, AND REPORTING IN MEDICAL DEVICE STUDIES**

Not applicable for this study.

## **10.8 APPENDIX 8: COUNTRY-SPECIFIC REQUIREMENTS**

### **CHINA**

For study participants enrolled from clinical sites in China, central confirmation of ER and PgR for screening eligibility will be performed (collection of the most recent archived FFPE biopsied tumor tissue samples at screening) as well as PK analysis (collection of blood sample on pre-dose D1 Cycle 2, Cycle 7, Cycle 13 and Cycle 25 using DBS and approximately 100 plasma samples aliquots kept from on C2 and/or C7 blood collection, to determine Blood/Plasma ratio).

Biological samples related to tertiary/exploratory (genetic analyses and biomarkers) endpoints will not be collected or analyzed. The impacted biological samples are:

- Collection of plasma sample for Molecular profiling in ctDNA in all study participants on predose D1 Cycle 1 and Cycle 2, and EOT in case of disease recurrence.
- Collection of blood sample for genomic DNA in all study participants on predose D1 Cycle 1.
- Collection of blood sample for future research on predose D1 Cycle 1 and Cycle 2, and EOT in case of disease recurrence.
- Collection of FFPE tissue sample at EOT in case of disease recurrence.
- Genetic analyses and biomarker research for FFPE tissue samples at screening (except that central confirmation of ER and PgR for screening eligibility will be performed).

## **10.9 APPENDIX 9: CONTINGENCY MEASURES FOR A REGIONAL OR NATIONAL EMERGENCY THAT IS DECLARED BY A GOVERNMENTAL AGENCY**

Continuation of the study in the event of a regional or national emergency declared by a governmental agency:

A regional or national emergency declared by a governmental agency (eg, public health emergency, natural disaster, pandemic, and terrorist attack) may prevent access to the clinical trial site.

Contingency procedures are suggested for an emergency that prevents access to the study site, to ensure the safety of the participants, to consider continuity of the clinical study conduct, protect trial integrity, and assist in maintaining compliance with GCP in Conduct of Clinical Trials Guidance. Sponsor agreement MUST be obtained prior to the implementation of these procedures for the duration of the emergency.

The decision for each individual participant to remain and/or start in the study should be made on a case by case basis based on best Investigator medical judgment. The clinical judgment of the treating physician should guide the management plan of each participant based on individual benefit/risk assessment and the evolving situation at the site ([Section 5.5](#)). However, in case new participant is eligible for the trial, the PI/site should assess the capacity to maintain these patients into the trial before any screening procedures will start. If the site cannot guarantee an accurate follow-up in the context of the trial, alternative treatment outside the clinical trial should be proposed.

### Study assessments and procedures

When participants are already randomized and/or treated, attempts should be made to perform all assessments in accordance with the protocol to the extent possible.

When possible, the focus should be on Investigational Medicinal Product (IMP) administration and safety blood collection (eg, biochemistry and hematology). However, all efforts should be made to perform the measurements of key parameters for efficacy endpoints (eg, tumor assessments). The deviations from the study protocol (eg, treatment delay, omission, tests not performed) should be documented in the source document and collected in the appropriate pages of the eCRF.

Procedures to be considered in the event of a regional or national emergency declared by a governmental agency:

- If onsite visits are not possible, remote visits (eg, with home nurses, home health vendor, mobile applications, etc) may be planned for the collection of possible safety and/or efficacy data (eg safety assessments, efficacy assessments especially the tumor assessment, PRO).
- If onsite visits are not possible, visit windows may be extended for assessment of safety and/or efficacy data that cannot be obtained remotely.
- Use of local clinic or laboratory locations may be allowed.
- The Direct-to-Patient (DTP) supply of the IMP from the PI/site where allowed by local regulations and agreed upon by participant. ([Section 1](#)).

Contingencies implemented due to emergency will be documented.

The impact of the regional or national emergency declared by a governmental agency on study conduct will be summarized (eg, study discontinuation or discontinuation/delay/omission of the intervention due to the emergency). Any additional analyses and methods required to evaluate the impact on efficacy (eg, missing data due to the emergency) and safety will be detailed in the SAP.

For a regional or national emergency declared by a governmental agency, contingency procedures may be implemented for the duration of the emergency. The participant or their legally authorized representative should be verbally informed prior to initiating any changes that are to be implemented for the duration of the emergency (eg, study visit delays/treatment extension, use of local labs) ([Section 10.1.9](#)).

## 10.10 APPENDIX 10: ADDITIONAL APPENDICES

### 10.10.1 Recommended dose modification guidelines for study treatment-related adverse event

Recommended dose modifications of study intervention (**Amcnestrant/Amcnestrant-matching placebo, Tamoxifen/Tamoxifen-matching placebo**) are presented in [Table 14](#).

**Table 14 - Recommended dose modification or discontinuation of study treatment-related toxicities**

NCI CTCAE v5 grade	Management of endocrine therapy (Amcnestrant/amcnestrant-matching placebo, Tamoxifen/tamoxifen-matching (placebo))
Toxicities	
Grade 1 or 2	No dose adjustment is required.
Grade 3 (if persisting despite optimal medical treatment)	Administer endocrine therapy if toxicity is not attributed to the IMP. If attributable, omit endocrine therapy until symptoms resolve to Grade ≤1, or Grade ≤2 (if not considered a safety risk for the patient). If resolved to Grade ≤1, or Grade ≤2 (if not considered a safety risk for the patient), resume the omitted endocrine therapy at the same dose. In case of first recurrence of the same Grade 3 event: administer at the same dose if restart is possible. In case of second recurrence of the same Grade 3 event: permanently discontinue IMP.
Grade 4	Administer endocrine therapy if toxicity is not attributed to the IMP. If attributable, omit endocrine therapy until symptoms resolve to Grade ≤1, or Grade ≤2 (if not considered a safety risk for the patient). If resolved to Grade ≤1, or Grade ≤2 (if not considered a safety risk for the patient), resume the omitted endocrine therapy at the same dose. If resolved to Grade 3: refer to Grade 3 instructions above. In case of first recurrence of the same Grade 4 event attributed to the IMP: permanently discontinue IMP.
Increase of ALT	
confounding factors such as, liver metastasis, hepato-biliary disorders, concomitant medications, etc. should be excluded prior to dose modifications	
Grade 0 or 1	No dose adjustment is required
Grade 2	Omit endocrine therapies administration until recovery to Grade ≤1, and then restart endocrine therapies at the same dose. In case of recurrence of the same Grade 2 event: administer at the same dose if restart is possible.
Grade 3	Omit endocrine therapies administration. Repeat LFTs within 2-3 days. If ALT levels not recovered, monitor LFTs weekly (or more frequently, if clinically indicated) until recovery to Grade ≤1 ALT increased (or baseline grade). On recovery, restart endocrine therapies at the same dose. In case of first recurrence of the same Grade 3 event: administer at the same dose if restart is possible. In case of second recurrence of the same Grade 3 event: permanently discontinue endocrine therapies.
Grade 4	Permanently discontinue study treatment

Liver function tests (LFTs) include AST, ALT, ALP (isoenzymes if Grade >2), total bilirubin (fractionated if >2 x ULN direct), GGT, and INR (if total bilirubin >2.5 ULN).

Grading according to CTCAE v5.0.

NCI CTCAE v5 = National Cancer Institute Common Terminology Criteria for Adverse Events version 5.0; LLN = lower limit of normal.

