### 8.2.3 Clinical safety laboratory assessments

- See Appendix 2 ([Section 10.2](#)) for the list of clinical laboratory tests to be performed and to the SoA ([Section 1.3](#)) for the timing and frequency.
- The Investigator must review the laboratory report, document this review, and record any clinically relevant changes occurring during the study. The laboratory reports must be filed with the source documents. Clinically significant abnormal laboratory findings are those which are not associated with the underlying disease, unless judged by the Investigator to be more severe than expected for the participant's condition. Laboratory abnormalities are to be recorded as adverse events only if they lead to treatment discontinuation and/or dose modification and/or fulfill a seriousness criterion and/or are defined as an AESI (see [Section 10.3](#), [Appendix 3]).

- All laboratory tests with values considered clinically significantly abnormal during participation in the study or within 30 days after the last dose of study intervention should be repeated until the values return to normal or baseline or are no longer considered clinically significant by the Investigator or medical monitor.
  - If such values do not return to normal/baseline within a period of time judged reasonable by the Investigator, the etiology should be identified, and the Sponsor or Sponsor's representatives notified.
  - All protocol-required laboratory assessments, as defined in Appendix 2 ([Section 10.2](#)), must be conducted in accordance with the laboratory manual and the SoA ([Section 1.3](#)).
  - If laboratory values from non-protocol specified laboratory assessments performed at the institution's local laboratory require a change in participant management or are considered clinically significant by the Investigator (eg, SAE or AE or dose modification), then the results must be recorded in the CRF.

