- LFTs include AST, ALT, ALP (isoenzymes if Grade  $> 2$ ), direct bilirubin, indirect bilirubin, GGT, and INR (if total bilirubin  $> 2.5$  ULN).
- An ultrasound, or other imaging of liver, should be considered based on the clinical presentation.
- A consultation with a hepatologist should be undertaken if there is,
  - Unexplained or persistent Grade  $\geq 3$  ALT despite dose omissions.
  - ALT  $> 3$  ULN and concomitant jaundice (total bilirubin  $> 2.5$  ULN), in patients with normal ALT and total bilirubin at baseline.
  - to exclude hepato-biliary disorders (eg, hepatotropic virus infections, autoimmune or alcoholic hepatitis, Non-Alcoholic Steatohepatitis, etc) or drug induced liver injury.
- Further hepatic virology will be undertaken as per the site's local guidelines for the treatment of cancer patients, considering the local and national recommendations.
- Photosensitivity
  - If photosensitivity is suspected in study participants, consider dermatologist consultation. Confounding factors such as other dermatological disorders, drug eruptions resulting from concomitant medication use, etc. should be excluded prior to any dose modification (refer to [Section 10.10.1](#) [Appendix 10] for treatment-related dose modification for non-hematological toxicities). In case of study intervention discontinuation because of photosensitivity reaction, study participant should be followed for possibility of development of other manifestations of photosensitivity such as photo-onycholysis, lichenoid reaction or actinic granuloma.

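### After a Grade 2 or 3 ALT rise, Table 14 restarts study treatment on ALT recovery alone; restart need not wait for the hepatologist consultation that section 8.3.6 advises

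*Combined protocol and SAP*

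**What the plan says.** **Table 14, Increase of ALT.** There are four rows. Grade 0 or 1 needs no adjustment. For Grade 2: "Omit endocrine therapies administration until recovery to Grade ≤1, and then restart endocrine therapies at the same dose". For Grade 3, treatment is omitted, liver tests are repeated within 2-3 days and then weekly if ALT has not recovered. Recovery is defined by ALT grade, and then: "On recovery, restart endocrine therapies at the same dose". Grade 4 is a permanent stop. The block opens with the note that "confounding factors such as, liver metastasis, hepato-biliary disorders, concomitant medications, etc. should be excluded prior to dose modifications". Bilirubin appears only in the footnote, as a component of the liver panel.

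**Table 14, general toxicity rows.** Grades 1 and 2 need no adjustment. For Grades 3 and 4 the rule is "If attributable, omit endocrine therapy until symptoms resolve to Grade ≤1, or Grade ≤2 (if not considered a safety risk for the patient"), and treatment then resumes at the same dose. A toxicity not attributed to study drug leads to no hold.

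**Section 8.3.6.** "A consultation with a hepatologist should be undertaken if there is" one of three situations: a Grade ≥3 ALT rise that is unexplained or persists despite omitted doses; ALT above 3 ULN with jaundice (total bilirubin above 2.5 ULN); or a need to exclude hepato-biliary disease or drug-induced injury. The second is restricted by the words "ULN), in patients with normal ALT and total bilirubin at baseline". The section refers the reader to the dose modification guidelines for managing ALT. Table 14 does not refer back.

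**Elsewhere.** Note a to Table 13 places the liver stopping criteria in sections 8.2.3 and 10.10.1. Section 8.2.3 has no ALT-with-bilirubin rule. It requires clinically significant values to be repeated and, if they have not normalised "within a period of time judged reasonable by the Investigator, the etiology should be identified, and the Sponsor" or its representatives notified. Appendix 6, "LIVER AND OTHER SAFETY: SUGGESTED ACTIONS AND FOLLOW-UP ASSESSMENTS", is marked not applicable.

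**The concern.** Section 8.3.6 treats raised ALT with raised bilirubin as a pattern needing specialist work-up, and drug-induced injury is among the diagnoses to be considered. Table 14, the operative rule for stopping and restarting, looks at ALT only. If ALT falls before bilirubin does, or before the hepatologist has reported, a site following Table 14 resumes the suspected drug at full dose.

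The design is double-dummy, so resuming study treatment always means resuming one active drug, and Table 1 lists hepatotoxicity as a risk for both. For tamoxifen it describes severe and some fatal liver cases, mostly of uncertain relationship, and notes that positive rechallenges have occurred. For amcenestrant it names jaundice and bilirubin among the signs to watch. What is at stake is the safety of re-exposure in a small number of participants, not the efficacy comparison.

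**Working it through.** The plan states no figure to reproduce. The check sets the rules side by side and asks whether any of them makes restart conditional on bilirubin or on the consultation.

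**Step 1. The ALT rows.**

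| ALT grade | Action | Bilirubin condition | Consultation condition |
|---|---|---|---|
| 0-1 | no adjustment | none | none |
| 2 | hold, restart at ALT Grade ≤1 | none | none |
| 3 | hold, restart at ALT Grade ≤1 or baseline grade | none | none |
| 4 | permanent stop | not needed | not needed |

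Rows with either condition: 0 of 4. Rows that restart: 2 of 4. The protocol does not print the CTCAE cut-offs, so the grade of an ALT just above 3 ULN is not known from the documents. This does not matter here, because neither the Grade 2 nor the Grade 3 row has the condition.

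**Step 2. Could the consultation be required elsewhere?** Section 8.3.6 advises it but does not tie it to restart. Section 6.5.2 requires contact with the sponsor or its representatives for retreatment only when a hold exceeds 28 days. Section 8.2.3 sets no restart rule, and Appendix 6 is not in use. The confounder note in the ALT block is the nearest candidate. It sets no bilirubin threshold and names no consultation, and excluding other causes makes drug injury more likely, not less. So no text makes restart wait for the consultation.

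**Step 3. Could bilirubin itself hold treatment?** It can, through the general rows. Let B be the unprinted lower limit of bilirubin Grade 3, in multiples of ULN, and consider a participant meeting the 8.3.6 trigger (bilirubin above 2.5 ULN).

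| Case | General row | Bilirubin part of the gap |
|---|---|---|
| B ≤ 2.5, rise attributed to study drug | hold to Grade ≤1, or ≤2 if judged no safety risk | mostly closed |
| B ≤ 2.5, rise not attributed | no hold | open |
| B > 2.5, bilirubin between 2.5 and B | no adjustment | open |
| B > 2.5, bilirubin at or above B, attributed | hold, as in the first case | mostly closed |

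It is only mostly closed because resumption at Grade 2 is allowed at the investigator's judgment. In no case does the general row require the consultation.

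**Step 4. Expedited reporting (conditional).** Section 8.3.6 lists four AESIs: pregnancy, symptomatic overdose, ALT Grade ≥3 and photosensitivity. None has a bilirubin component (0 of 4). Let G be the assumed lower limit of ALT Grade 3, in multiples of ULN. The trigger starts at ALT 3 ULN, so the band outside the AESI list has width max(0, G − 3):

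- G ≤ 3: 0, so every case is already an AESI.
- G = 4: 4 − 3 = 1 ULN.
- G = 5: 5 − 3 = 2 ULN.

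Table 1 describes ALT rises of at least 2 × ULN that were all Grade 1. That makes G above 3 plausible but does not establish it.

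**Step 5. Scheduled panels.** With 28-day cycles, the planned gaps are 3 × 28 = 84 days for the 12-weekly visits up to C28, 6 × 28 = 168 days from C28 to C58, and 8 × 28 + 30 = 254 days from C58 D1 to the end-of-treatment visit.

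**The case against.** The strongest reply is that the plan already surrounds this case with safeguards. Table 14 is headed as recommended. Section 7.1.1 lets the investigator stop for any adverse event that warrants it. Section 6.5.2 speaks of recovery from the toxicity, which can be read to include jaundice. Section 8.2.3 requires significant values to be repeated. Section 8.3.6 asks for liver tests on unexplained jaundice, nausea, right upper abdominal pain, fever or rash, and names drug-induced injury as a reason to consult. The general rows of Table 14 can hold treatment for bilirubin in its own right. E 20 excludes impaired liver function at entry, the IDMC reviews safety about every six months, and Table 1 reports no amcenestrant-related hepatotoxicity in AMEERA-1.

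All of this is correct, and it narrows the point. It rules out three stronger readings that a reader might infer:

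- That the plan never acts on bilirubin. The general rows do for an attributed Grade 3-4 rise.
- That a participant could go unmonitored for 84, 168 or 254 days after restart. Those are maximum gaps between scheduled panels. Restart comes after a hold, so less of the interval remains, and a known abnormal value falls under the repeat-testing rule of section 8.2.3, although that rule gives no interval.
- That such an event would go unreported. A laboratory abnormality leading to dose modification is recorded as an adverse event, omission dates go in the CRF, and the event may qualify as serious. Only the 24-hour AESI route is in question, and only if ALT Grade 3 starts above 3 ULN.

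None of these safeguards makes restart conditional on the consultation. Freedom to stop is not a restart condition, and where Table 14 addresses the case its instruction is to resume.

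**Conclusion.** The concern holds in a limited form. The missing consultation condition follows from the text alone and needs no assumption about grading. The missing bilirubin condition depends on a cut-off the documents do not print: it is mostly closed for an attributed rise if 2.5 ULN reaches Grade 3, and open if 2.5 ULN is Grade 2. The AESI question is conditional on the ALT cut-off and is secondary.

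The size is small. The documents give no rate for the combined pattern. Table 1's only amcenestrant liver findings in humans are three healthy subjects with transient Grade 1 ALT rises, so few cases are expected. The sample size and the primary analysis are unaffected. The correction is still worth making at the next amendment, because two sections of the protocol give unconnected instructions on re-exposure after possible drug-induced liver injury. Confidence is moderate.

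**What to change.** Add one row to the ALT block of Table 14 for ALT > 3 ULN with total bilirubin > 2.5 ULN in participants with normal ALT and total bilirubin at baseline. Hold study treatment, and do not restart until ALT is Grade ≤1, total bilirubin is normal and the section 8.3.6 hepatologist consultation is complete. Permanent discontinuation at ALT Grade 4 is unchanged.

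Optionally, if ALT Grade 3 starts above 3 ULN, list the same pattern as an AESI in section 8.3.6 so that it is reported within 24 hours.

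**Cost.** One table row and, if the option is taken, one AESI term in the eCRF. No new tests or scheduled visits are needed, since bilirubin is already in the Table 13 chemistry panel. Holds may be longer in the few participants affected, particularly where a hepatologist is hard to reach, and the AESI option would add a few expedited reports.

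**Limit.** Participants with ALT or bilirubin above normal at baseline stay outside the new row, as they are outside the section 8.3.6 trigger now. The baseline condition should be kept. E 20 admits participants with Gilbert's disease with total bilirubin up to 3.0 × ULN, which is 3.0 − 2.5 = 0.5 × ULN above the trigger, so without that condition their usual bilirubin could meet the bilirubin part of the rule.
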